#### **INTRODUCTION**

#### **List of Abbreviations:**

Implant placement (IP) Marginal Bone level changes (MBL) Probing pocket depth (PPD) Bleeding on Probing (BOP) Group Short (GS): Experimental Group Group Long (GL): Control Group

#### **BACKGROUND and SIGNIFICANCE**

Edentulism is a condition of being toothless, which impacts the patient's ability in performing some daily tasks and affects their esthetic appearance and self-confidence (Misch, 2007). Prostheses supported by dental implants can improve patients' quality of life by providing a pleasant appearance as well as comfort in speaking and chewing (Sargozaie et al., 2017). After extraction, the bony socket undergoes significant horizontal and vertical resorption especially in the maxillary posterior area (Chappuis et al., 2017). These changes often lead to more complex and time-consuming procedures, such as a lateral or transcrestal sinus lift, for placing implants in the area. Despite the reliability of these techniques, providers are faced with challenges such as elevated cost, higher morbidity, and more intra- and post-surgical complications. These challenges may be overcome by utilizing less invasive procedures such as short implants. However, the definition of a short dental implant remains a topic of controversy. According to Striezel & Reichart, an implant with a length of  $\leq 11$  mm is considered short (Strietzel and Reichart, 2007) whereas some authors consider a short implant to be <10 mm (Mezzomo et al., 2014, Telleman et al., 2014) or <8 mm (Fan et al., 2017). Additionally, an implant with a length of <6.5 mm has been defined as extra-short (Anitua et al., 2014, Anitua et al., 2015). During the last decade, short implants have shown to be a reliable and effective alternative solution for patients with bone atrophies (Pieri et al., 2017). Indeed, it has been demonstrated that unfavorable crown to implant (C/I) ratio is not related to increased biological complications or implant failure (Garaicoa-Pazmino et al., 2014). However, prevalence of peri-implantitis could present a greater concern due to the limited length, especially for people with previous history of periodontitis. A recent meta-analysis on short implants versus standard implants in the posterior jaw that included 13 studies with 1269 patients and 2631 implants showed no significant difference in implant survival, marginal bone loss, complications, or prosthesis failure. Nevertheless, it was

concluded that short implants with <8 mm should be used with caution because they present a higher risk of failure as compared to standard-length ( $\geq$ 8mm) implants (Lemos et al., 2016). In a systematic review based on the evaluation of 8 randomized controlled clinical trials (RCTs), the European Academy of Osseointegration (EAO) Consensus Conference in 2015 noted that longer dental implants in the augmented sinus caused a higher number of biological complications, increased morbidity, costs and surgical time. Therefore, shorter dental implants may be the preferred treatment alternative (Thoma et al., 2015). A recent multicenter, randomized, controlled clinical trial found that short implants (6 mm) for single-tooth restorations in the posterior maxilla were a viable solution versus longer implants ( $\geq$ 10mm) in combination with sinus lift. After three years of follow-up and with a residual ridge height of 5–7 mm, no implants were lost in both groups and no statistically significant difference in prosthetic complications were reported (Pohl et al., 2017). All these studies excluded patients with a previous history of periodontitis.

#### **OBJECTIVES OF THE STUDY**

The purpose of this study is to evaluate clinical and radiological parameters of 5 mm short implants (GS) compared to longer implants (GL) (10 mm) placed in sinus-grafted sites.

Null Hypothesis (H0): There are no statistically significant clinical or radiographic outcome differences between the two groups, GS and GL.

Alternative Hypothesis (H1): There are statistically significant clinical or radiographic outcome differences between the two groups, GS and GL.

#### STUDY DESIGN

The present study will be a parallel, randomized single center clinical trial performed according to the CONSORT statement (http://www.consort-statement.org/).

Two different treatment modalities, GS and GL, will be compared in this randomized clinical trial. GS subjects will receive a short dental implant (5 mm in length) with no sinus lift whereas GL subjects will receive a 10 mm long implant after sinus lifting with allograft. The flow chart of the study is presented in Fig. 1.

Fig. 1 CONSORT flow chart of the study

The Institutional Review Board (IRB) for the Medical Sciences at the University of Michigan, Ann Arbor, MI, must review and approve this study before enrollment of participants begins. It is the responsibility of the investigator to assure that all aspects of the institutional review are conducted in accordance with current Federal Regulations. A letter with IRB approval for the protocol must be received by the Principal Investigator before the initiation of the study. Amendments to the protocol will be subject to the same requirements as the original protocol. At each annual protocol renewal, an updated report of the numbers of samples and any adverse events will be provided to the IRB.

After completion or termination of the study, the investigator will submit a final report to the IRB. This report should include any deviations from the protocol, the number of patients evaluated, adverse events, and a conclusion summarizing the results. This study will also be registered on ClinicalTrials.gov. In addition, the study will be conducted according to the principles outlined in the Declaration of Helsinki on experimentation involving human subjects, as revised in 2000. Partially edentulous patients requiring an implant to replace a missing tooth in the maxillary premolar, 1st molar, or 2nd molar area with bone crest height more than 5 mm but less than 8 mm will be recruited for this trial. Up to 50 patients will be enrolled (half randomized for each group) in the Periodontics and Oral Medicine clinic at the University of Michigan School of Dentistry, Ann Arbor, Michigan. A signed, written informed consent must be obtained from each subject before he or she enters the study after he or she has been given verbal and written information describing the nature and duration of the study. Subjects will be consented in a private cubicle inside the Periodontics and Oral Medicine clinic. An investigator or study coordinator will give the consent document to the potential subject and answer any questions the subject has before and after they read the consent document. Subjects will be given ample time to read the form and ask questions before they sign. The signed informed consent will be retained with the study records. Each subject will also be given a copy of his/her informed consent.

Patients that meet the inclusion/exclusion criteria and consent to the research study will receive a dental implant at no cost and an implant crown at reduced cost to replace their missing tooth. Research subjects will be followed for 24 months ( $\pm 1$  month) after implant placement, for a total of 23-26 months (see Appendix A: Schedule of Events) for the entire study. Subjects will complete 10 research visits as described in the Study Procedures.

#### Primary and secondary endpoints

Primary endpoint: Comparing mesial-distal (M-D) bone loss between the two groups (Radiologic outcome)

Secondary endpoints: Clinical outcomes and Patient reporting outcomes

- 1. Determine the survival rate and success rate of the Group Short (GS) and Group Long (GL) group.
- 2. Compare incidence and types of surgical and prosthetic complications between groups
- 3. Compare the number of sites with bleeding on probing (BOP)
- 4. Compare the cost of both procedures and the cost of the prosthetic complications
- 5. Compare the probing pocket depth (PPD)
- 6. Determine the pain after treatment: Visual analog score (VAS)
- 7. Compare patient satisfaction
- 8. Compare surgical time

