3 = Moderate, bright surface inflammation, erythema, edema and/or hypertrophy of gingival marginal or papillary

4 = Severe inflammation: erythema, edema and/or marginal gingival hypertrophy of the unit or spontaneous bleeding, papillary, congestion or ulceration.

- Prosthesis failure: Planned prosthesis which could not be placed due to implant failure(s), loss of the prosthesis secondary to implant failure(s), or replacement of the definitive prosthesis for any reason.
- Implant failure: It will be defined as implant mobility (assessed from force applied with two hand instrument), pain, or neuropathy.
- Implant success: It will be defined as 1) Absence of persistent subjective complaints such as pain, foreign body sensation and/or dysesthesia 2) Absence of a peri-implant infection with suppuration 3) Absence of mobility 4) Absence of a continuous radiolucency around the implant and 5) Absence of any biological or prosthetic complications (Buser et al., 2012)
- Peri-implantitis: It will be defined as detectable radiographic bone loss beyond the initial biological bone remodeling.

2) The following measurements will be taken for each treated implant by a blinded, calibrated examiner after implant placement, 12-month follow-up, and 24-month follow-up.

Bone thickness (BT): It will be determined based on CBCT and expressed as the distance from the most coronal bone-implant contact to the outer surface of the buccal plate. The mean values will be calculated for each implant.

3) The following measurements will be taken for each treated implant by a blinded, calibrated examiner at prosthetic placement, 12-month follow-up, and 24-month follow-up.

- Crown to implant ratio: The height of the crowns will be measured on the radiographs from the implant-abutment interface to the most coronal point on the crown. The anatomical crown-to-implant ratio (anatomical C/I ratio) will then be calculated dividing the anatomical crown by the length of the implant.4)
- 4) ISQ (Implant stability quotiant) will be measured at the time of healing abutment placement.

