#### **Implant Related Risks**

- 1) Implant Failure
- 2) Biologic complications such as sinus membrane perforations, persistent bleeding, sinusitis (or acute sinus infection), rupture of sinus membrane, soft tissue (graft) dehiscence, abscess, pus, pain, swelling, peri-implant mucositis (heavily inflamed soft tissue without bone loss), or peri-implantitis (bone loss around the implant).
- 3) Prosthetic complications such as fixed prosthetic device detachment, loosening of abutment screws or healing caps, and fracture of the screw, framework, or occlusal material.

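### Secondary endpoint 2 leaves biological complications, including peri-implantitis, out of the only by-arm comparison of complication incidence and types

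*Combined protocol and SAP*

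**What the plan says.** In *Primary and secondary endpoints*, secondary item 2 is to "Compare incidence and types of surgical and prosthetic complications between groups". No other endpoint concerns the incidence and types of complications. Item 1 is to "Determine the survival rate and success rate of the Group Short (GS) and Group Long (GL) group".

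*Clinical measurements* defines implant success by five conditions, among them "Absence of a peri-implant infection with suppuration" and "Absence of any biological or prosthetic complications". The same list gives a definition of peri-implantitis: "It will be defined as detectable radiographic bone loss beyond the initial biological bone remodeling".

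*Implant Related Risks* has three entries: implant failure, biologic complications and prosthetic complications. The biologic entry starts with sinus membrane perforation, includes sinusitis, abscess and pus, and ends with "peri-implant mucositis (heavily inflamed soft tissue without bone loss), or peri-implantitis (bone loss around the implant".

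*Background and Significance* says that "prevalence of peri-implantitis could present a greater concern due to the limited length", and adds that this applies especially to people who have had periodontitis. It also cites a consensus review in which longer implants in the augmented sinus had more biological complications.

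*Statistical Considerations* mentions complications once, as prosthetic complications to be related to the crown-implant ratio. It gives no method for comparing complication proportions between the arms.

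**The concern.** Late disease of the tissue around an implant is neither an event of the operation nor a fault of the crown. Read literally, item 2 therefore does not count it. Yet the background gives a reason to look for such disease in each arm: implant length in the short group, the augmented sinus in the long group. A report that followed the plan could state complication incidence by arm and say nothing of mucositis, peri-implantitis, abscess or late dehiscence, although the data to describe them are collected. At stake is what the trial can conclude about complications, not its primary result.

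**Working it through.** **1. The classes, side by side.**

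| Section | Classes used | Where peri-implantitis falls | Where perforation and sinusitis fall |
|---|---|---|---|
| Endpoints, item 2 | surgical, prosthetic | neither | surgical, or not covered |
| Clinical measurements, success definition | biological, prosthetic | biological | not stated |
| Implant Related Risks | failure, biologic, prosthetic | biologic | biologic |
| Post-surgical instructions | surgical (examples: infection, pain, other adverse events) | not stated | not stated |

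Item 2 has a surgical class that the risk list lacks, and lacks the biological class that both the risk list and the success definition use. Infection is an example of a surgical complication in one section, while sinus infection and abscess are biologic in another.

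**2. What the other endpoints can show.**

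- Success rate (item 1): a biological event makes the implant a non-success, so it is counted. But a case of peri-implantitis and a loose screw count alike. The composite gives no types, and the stated aim is to determine the rate in each group, with no comparison specified.
- Bleeding on probing (item 3) and probing depth (item 5): compared by arm, but as site counts and depths, not cases. They do not register abscess, pus or dehiscence.
- Primary endpoint, "Comparing mesial-distal (M-D) bone loss between the two groups (Radiologic outcome": the measurement on which the peri-implantitis definition rests, but summarised as a group mean.

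**3. How far a few cases move the mean.** Shift in arm mean = cases × extra loss ÷ n. Assume 2 cases, each with 2 mm of extra loss (range 1-3 mm). Neither figure is in the documents.

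- n = 17: 2 × 2 ÷ 17 = 0.24 mm (range 0.12 to 0.35).
- n = 25: 2 × 2 ÷ 25 = 0.16 mm (range 0.08 to 0.24).

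All of these lie below the 0.5 mm difference that the trial is powered to detect.

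**4. Number of patients involved.** The documents give no complication rate. With 10% assumed (range 5-20%): 0.10 × 17 = 1.7 and 0.10 × 25 = 2.5 per arm; the extremes are 0.05 × 17 = 0.85 and 0.20 × 25 = 5. The same rate is applied to both arms, so this shows how many events fall outside item 2, not a difference between arms.

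**5. What an added comparison could detect.** The stated minimum of 17 per arm is for bone loss and has no stated SD, so it cannot be reproduced from the text. An assumed SD of 0.48 mm, two-sided, gives 2 × (1.960 + 0.842)² × 0.48² ÷ 0.5² = 14.5, so 15 per arm, and 15 ÷ 0.9 = 16.7, so 17. Nothing below depends on that SD.

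For proportions, power is the summed binomial probability of all tables with a two-sided Fisher p-value of at most 0.05. The n for 80% power is [1.960 √(2p̄q̄) + 0.842 √(p₁q₁ + p₂q₂)]² ÷ (p₁ − p₂)², where p̄ is the mean of the two rates.

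| Assumed rates | Power, 17 per arm | Power, 25 per arm | n per arm for 80% |
|---|---|---|---|
| 5% v 20% | 12% | 20% | 76 |
| 10% v 30% | 19% | 31% | 62 |

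With a continuity correction the last column becomes 88 and 72. The trial can describe biological complications by arm but cannot test them.

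**The case against.** The strongest reply is that the trial does follow this disease process. Bone loss is the primary endpoint, bleeding and probing depth are compared, and any biological complication makes an implant a non-success. Adverse events are also marked in the schedule at every visit from V2 to V10. All of this is correct, and it rules out saying that an excess in one arm would be missed altogether. What remains is that none of these gives the incidence and types of biological events by arm, which is the purpose of item 2.

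A reader might go further and infer that item 2 is tilted towards the short implants because their main hazard goes uncounted. The documents do not support this, for three reasons.

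- The background's remark on peri-implantitis is conditional and is qualified by a history of periodontitis. The same section reports a meta-analysis with no significant difference in marginal bone loss or complications. Its firmer caution about implants under 8 mm concerns failure, which item 1 covers.
- The background also attributes more biological complications to longer implants in the augmented sinus. On that evidence the omission could favour the long arm.
- The direction depends on the meaning of surgical. If perforation and sinusitis count as surgical, sinus-lift harms enter item 2 and late peri-implant disease does not. If the risk list governs, perforation and sinusitis are biologic and drop out as well, so item 2 misses harms specific to the long arm.

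It is also fair to object that adding a word to item 2 is not enough. The peri-implantitis definition names no reference radiograph and no measurement threshold, and mucositis has only a short gloss in the risk list. Cases could not be scored reproducibly as the text stands. This objection is sound, and the fix has to meet it.

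**Conclusion.** The point stands as a gap in the secondary endpoints. Biological complications are recognised as a class and feed the composite success rate, but their incidence and types are never compared by arm. The boundary between surgical and biological events is also left open, so it could be drawn after the data are known. Which arm the omission favours cannot be determined from the documents.

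The gap is small in absolute terms: about 1.7 to 2.5 patients per arm at an assumed 10% (0.85 to 5 over the range 5-20%). These rates, and those behind the power figures, are assumptions. The omission itself rests only on the text. The primary analysis and sample size do not change.

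**What to change.** 1. Reword item 2 to cover three classes: surgical, biological (with peri-implant mucositis and peri-implantitis named) and prosthetic.
2. Assign each event in *Implant Related Risks* to exactly one class before the data are seen, and bring the success definition and the post-surgical instructions into line.
3. Have the sponsor state the reference radiograph and the measurement threshold for the peri-implantitis definition, and how a mucositis case is scored.
4. Report, by arm, patients with at least one event in each class and in total, with the risk difference and an exact or score 95% confidence interval, labelled descriptive.

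The cost is a revised endpoint line, a short case definition and one table. No visit or procedure is added: the schedule already has adverse events at V2 to V10, and clinical measurements and standardized radiographs at V8 and V10. The downside is one more unpowered secondary comparison.

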#### Participants

50 patients satisfying the following inclusion criteria will be recruited:

- Age 20 years or older at enrollment
- Able to provide informed consent
- Systemically healthy patients

- Full-mouth plaque score and full-mouth bleeding score ≤ 30% (measured at four sites per tooth)
- Missing one premolar, 1st molar, or 2nd molar in the maxillary arch (Minimum healing time after extraction: ≥4 months)
- One neighboring tooth or implant restoration must be present to the implant site.
- Presence of natural tooth/teeth, partial prosthesis and/or implants in the opposite jaw in contact with the planned crown/s deemed by the investigator as likely to present an initially stable implant situation
- Residual bone height under the maxillary sinus more than 5 mm but less than 8 mm and a width of at least 7 mm, as measured on cone beam computer tomography (CBCT) scans.

Exclusion criteria are:

- Unlikely to be able to comply with study procedures
- Uncontrolled pathologic processes in the oral cavity
- History of allergic reactions to dental local anesthetics
- History of head and neck chemotherapy or radiation within 5 years prior to surgery
- Systemic or local disease or condition that could compromise post-operative healing and/or osseointegration, such as HIV infection, Paget's disease, osteoporosis, etc.
- Uncontrolled diabetes mellitus (HbA1c >8)
- Patients taking corticosteroids, IV bisphosphonates, or any other medication that could influence post-operative healing and/or osseointegration
- Smokes more than 10 cigarettes/day
- Present alcohol and/or drug abuser (self-reported)
- Pregnant, unsure pregnancy status, or lactating females (self-reported), or planning to become pregnant within 1 year of study enrollment
- Any medical conditions that may affect the outcome of the study.

## INVESTIGATIONAL PRODUCT OVERVIEW

## Implants

- *GS* T3 Short External Hex with DCD 5.0 mm Length Implants; Zimmer Biomet (Zimmer, Palm Beach Gardens, Florida, US)
- *GL* T3 with DCD External Hex Parallel Walled x 10 mm Length Implants; Zimmer Biomet (Zimmer, Palm Beach Gardens, Florida, US)

#### **STUDY PROCEDURES**

#### **Clinical measurements**

1) The following measurements will be taken for each treated implant by a blinded, calibrated examiner at the implant placement (surgery V2), at the time of prosthetic placement (5-month postop V6), 12-month follow-up (V8), and 24-month follow-up (V10).

- Marginal bone level (MBL): It will be calculated based on standardized radiographs using registered bite-block with a Rinn (Dentsply Rinn, Elgin, IL, USA) film holder and expressed as the distance from the implant shoulder to the most coronal bone-to-implant contact (BIC) on the mesial and distal side of the implant. The mean values will be calculated for each implant at the time of implant placement, at the time of prosthetic placement (5-month post-op V6), 12-month follow-up (V8), and at 24-month follow-up (V10). In the case that the bone levels around the study implants are hidden or difficult to read, new radiographs will be taken. Peri-implant marginal bone levels will be measured using the ImageJ software\* (ImageJ, U. S. National Institutes of Health, Bethesda, Maryland, USA) (Schneider et al., 2012). The software will be calibrated for every single image using the known implant length or the length of the implant collar. Measurements of the mesial and distal bone crest level adjacent to each implant will be rounded to the nearest 0.1 mm. Implants with bone up to the coronal margin of the implant collar will be given a value of zero. Mesial and distal measurements of each implant are averaged, and a mean calculated at patient level and then at group level.
- PPD and BOP: It will be assessed at 4 sites per implant (mesial, distal, buccal, and palatal) with a measurement stent using a periodontal probe (UNC, Hu-Friedy, Chicago, IL, USA). PPD are measured from the distance of the mucosal margin to the bottom of the probable pocket in mm. BOP is recorded using the following scoring method: 0) no bleeding 1) an isolated bleeding spot is visible, 2) blood forms a confluent red line on margin, and 3) heavy or profuse bleeding.
- Plaque: The level of oral hygiene will be evaluated using the Modified gingival index (Lobene et al., 1986) (Scores 1-4).

0 = Absence of inflammation

1 = Mild inflammation or with slight changes in color and texture but not in all portions of gingival marginal or papillary

2 = Mild inflammation, such as the preceding criteria, in all portions of gingival marginal or papillary

3 = Moderate, bright surface inflammation, erythema, edema and/or hypertrophy of gingival marginal or papillary

4 = Severe inflammation: erythema, edema and/or marginal gingival hypertrophy of the unit or spontaneous bleeding, papillary, congestion or ulceration.

- Prosthesis failure: Planned prosthesis which could not be placed due to implant failure(s), loss of the prosthesis secondary to implant failure(s), or replacement of the definitive prosthesis for any reason.
- Implant failure: It will be defined as implant mobility (assessed from force applied with two hand instrument), pain, or neuropathy.
- Implant success: It will be defined as 1) Absence of persistent subjective complaints such as pain, foreign body sensation and/or dysesthesia 2) Absence of a peri-implant infection with suppuration 3) Absence of mobility 4) Absence of a continuous radiolucency around the implant and 5) Absence of any biological or prosthetic complications (Buser et al., 2012)
- Peri-implantitis: It will be defined as detectable radiographic bone loss beyond the initial biological bone remodeling.

2) The following measurements will be taken for each treated implant by a blinded, calibrated examiner after implant placement, 12-month follow-up, and 24-month follow-up.

Bone thickness (BT): It will be determined based on CBCT and expressed as the distance from the most coronal bone-implant contact to the outer surface of the buccal plate. The mean values will be calculated for each implant.

3) The following measurements will be taken for each treated implant by a blinded, calibrated examiner at prosthetic placement, 12-month follow-up, and 24-month follow-up.

- Crown to implant ratio: The height of the crowns will be measured on the radiographs from the implant-abutment interface to the most coronal point on the crown. The anatomical crown-to-implant ratio (anatomical C/I ratio) will then be calculated dividing the anatomical crown by the length of the implant.4)
- 4) ISQ (Implant stability quotiant) will be measured at the time of healing abutment placement.

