#### Randomization and masking of examiners

The randomization of the patients to either the test (5-mm implant) or control group (10-mm implant) is determined using a computer-generated randomization list (www.random.org). After administration of a local like 2% Lidocaine with 1:100k epinephrine, sulcular incisions at the adjacent teeth and a midcrestal incision will be performed, allowing reflection of a full-thickness flap. At this stage, the randomization concealment will be broken, and the surgical site will be prepared according to the manufacturer's instructions.

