#### Experimental group (GS)

5.0 mmL x 5.0mmD Zimmer T3 Short Ex Hex With Discrete Crystalline Deposition (DCD) implants:

1. Crestal incision and flap elevation

- 2. ACT Short Pointed Started Drill will be used to penetrate the cortical bone to the first depth mark on the drill. The recommended drill speed is 1200-1500 rpm. Copious irrigation with sterile saline solution is planned to prevent overheating of the bone during high speed drilling.
- 3. 2.0 mm ACT Short Twist Drill will be to drill to the bottom of the depth mark for 5.0 mm length implants. The recommended drill speed is 1250 rpm.
- 4. The direction and position of the preparation is verified by inserting the narrow end of the direction indicator into the osteotomy. A suture will be threaded through the hole to prevent accidental swallowing.
- After proper alignment is verified using the Direction indicator, the 3.25 mm ACT Short Twist Drill will be used to drill until the bottom of the depth mark for 5 mm implants with a speed 1250 rpm.
- Once the coronal aspect of the osteotomy has been prepared the 3.85mm ACT Short Twist Drill will be used to Drill to the bottom of the depth mark for 5.0mm. The recommended drill speed is 1250 rpm.
- The 3.85 mm Short Shaping Drill with a yellow band indicating that it is for use with a 5.0mmD T3 Short Implants. The recommended drill speed is 1250 rpm.
- Tapping Step for dense bone (Type I) using the Handpiece Connector advancing the tap into the prepared site at approximately 15-20 rpm. Final seating of the Short Dense bone Tap may require the use of the Ratchet Extension and the Ratchet Wrench.
- 9. The implant will be placed into the prepared site at approximately 15-20 rpm. Final seating of the implant may require the use of a Ratchet Extension and Ratchet Wrench.
- 10. To remove the implant mount, Open End Wrench will be placed onto the mount. The screw is loosened at the top of the mount with a Large Hex Driver or Large Hex Driver Tip inserted into the Right-Angle Driver or Low Torque Indicating Ratchet Wrench and rotate counter-clockwise. After the screw is completely loosened, the Open End Wrench will be rotated counter-clockwise slightly before removing the mount. The mount can be carried from the mouth with the Open End Wrench.
- 11. Cover Screw from the No-Touch Implant Tray with the Small Hex Driver (PHD00N) is placed onto the implant at no more than 10 Ncm.
- 12. Soft-tissue flaps will be secured and repositioned with sutures.

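### The examiner who reads the primary bone level is called blinded, but the plan gives no step that hides the arm, and a film of the whole implant shows it

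*Combined protocol and SAP*

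**What the plan says.** All references are to the combined protocol and SAP.

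- **Primary and secondary endpoints.** The primary endpoint is "Comparing mesial-distal (M-D) bone loss between the two groups (Radiologic outcome").
- **Clinical measurements, item 1.** Marginal bone level (MBL) is the distance from the implant shoulder to the first bone-to-implant contact, read on standardized films at four time points. On the reader: "The following measurements will be taken for each treated implant by a blinded, calibrated examiner at the implant placement (surgery V2"), with the later visits following. On scaling: "The software will be calibrated for every single image using the known implant length or the length of the implant collar".
- **Study Design.** For the experimental arm the section states: "GS subjects will receive a short dental implant (5 mm in length) with no sinus lift". For the control arm it states: "GL subjects will receive a 10 mm long implant after sinus lifting with allograft".
- **Experimental group (GS) and Control group (GL).** The short implant is "5.0 mmL x 5.0mmD Zimmer T3 Short Ex Hex". The long implant is 10 mm by 5.0 mm, from the parallel-walled line.
- **Clinical measurements, items 2 and 3.** CBCT bone thickness and the crown-to-implant ratio, which divides by implant length, are also given to a blinded, calibrated examiner. The text does not say whether this is the same person.
- **Randomization and masking of examiners.** The section covers the computer-generated list and the moment after flap reflection: "At this stage, the randomization concealment will be broken". It contains no masking step for any examiner.
- **Data Management.** Group identification goes to the investigator when the study ends.

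**The concern.** A reader of the trial report will take 'blinded' to mean that whoever measured the primary outcome did not know the arm. Here the treatment is the length of the object being measured. Withholding the allocation list does not protect a reading if the film displays the allocation.

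Locating the first bone contact by hand and recording it to 0.1 mm needs some judgement, as does deciding that a film is too unclear and must be retaken. If that judgement shifted with knowledge of the arm, and shifted differently at baseline and follow-up, the comparison of bone loss would be affected. The protocol limits discretion through bite-block films, a defined landmark and retakes of unreadable films, but none of these hides the arm.

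**Working it through.** **1. Does a film reveal the arm?** Inputs are the implant dimensions in the two surgical sections. Length divided by diameter is 5.0/5.0 = 1.0 in GS and 10/5.0 = 2.0 in GL. The outline alone separates the arms, without any scale or list, and the grafted sinus is a second cue.

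**2. Does the plan use films of the whole implant?** It does not say so directly. Two scaling references are allowed:

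| Reference | View needed | Does it reveal the arm? |
|---|---|---|
| Known implant length | Whole implant | Yes: the person scaling enters 5 or 10 mm |
| Collar length | Coronal part is enough | Not through length, if the image is cropped |

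No section says that the collar is always used, or that images are cropped, coded or scaled by someone other than the reader. A whole-implant film is therefore a strong inference, not stated text.

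**3. Does another section supply the masking?** The section headed for masking of examiners gives none. The data-management rule at most keeps the list from the reader. The CBCT and crown-to-implant readings are a second route: an examiner who does them before or alongside MBL learns the arm even if the MBL films are cropped.

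**4. What could be at stake?** The documents give no figure for reading error or masking, so this is illustration only.

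- From the documents: 17 per arm and a 0.5 mm target difference (Statistical Considerations); up to 50 patients, hence 25 per arm (Study Design); alpha 0.05.
- Assumed: SD 0.4-0.6 mm, because none is stated; a two-sided test; a net differential shift d; no true difference; a two-sample t-test in place of the planned repeated-measures ANOVA. The SD range includes the 0.46-0.47 mm at which a t-test calculation returns 17 per arm (15 before dropout; 15/0.9 = 16.7).
- Formula: noncentrality = d / (SD × √(2/n)). The rejection probability is the two-tailed area of the noncentral t with 2n − 2 degrees of freedom beyond the critical value.
- With d = 0.1 mm, n = 17, SD 0.6: 0.1/(0.6 × √(2/17)) = 0.486; critical value 2.037; rejection probability 0.076.
- With d = 0.1 mm, n = 25, SD 0.4: 0.1/(0.4 × √(2/25)) = 0.884; critical value 2.011; rejection probability 0.139.

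The assumed 0.1 mm equals the rounding unit and is 0.1/0.5 = 20% of the target difference. It moves the false-positive rate from 5% to about 8-14%. The direction is unknown, so power could fall or rise: for a true 0.5 mm at n = 17 and SD 0.6, power is 0.654 with no shift, 0.470 with an opposing 0.1 mm and 0.807 with an aligned one.

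**The case against.** The strongest reply is that silence about method does not prove that the reader is unmasked. The protocol says the examiner is blinded, MBL is a coronal distance, and collar scaling is compatible with an image that never shows the apex. This stands in part. A reader might infer that the MBL reading is certainly unmasked, and the documents do not go that far. They support a narrower statement: no masking step is described, one of the two permitted scaling methods identifies the arm, and any whole-implant film shows it.

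A second reply is that nothing shows bias. That also stands. A reader might take the 8-14% as an estimate of the trial's error rate, but both the shift and the SD are assumed. A constant arm-related offset would cancel in change from baseline. That argument has limits of its own: the plan names repeated-measures ANOVA without defining a change score, and bone reaching the collar margin is scored zero, so an offset need not be equal at baseline and follow-up.

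A third reply is that implant length is the intervention, so some visibility is unavoidable. This holds for the whole film, but not for the short coronal segment that MBL needs. The two implants come from different product lines, however, and the documents do not say whether they look alike coronally. Cropping may therefore mask only partly.

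**Conclusion.** The point holds and should be fixed. The plan states a protection for its primary reading and describes nothing that delivers it; a film of the whole implant would defeat it. The same gap affects the CBCT bone thickness and crown-to-implant readings.

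That the films show the whole implant is inferred from the permitted length scaling and from the absence of any cropping rule. No size or direction of bias can be derived from the documents, and no claim that the primary result will be biased is supported. The false-positive figures only show how sensitive a trial of 17-25 per arm would be if a differential shift of the assumed size occurred.

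**What to change.** 1. The study coordinator, not the MBL reader, sets the ImageJ scale on the full image by one rule fixed in advance. Known implant length can be kept. An assumed 0.1 mm marking error is 1-2% of a 10 or 5 mm implant, but 5-10% of a collar assumed to be 1-2 mm long.
2. The coordinator then gives the reader coded images cropped to the same coronal depth in both arms, less than 5 mm below the shoulder. This leaves out the GS apex. If the shoulder lies near the crest (assumed), it also leaves out the sinus floor, because eligibility requires "Residual bone height under the maxillary sinus more than 5 mm but less than 8 mm".
3. All MBL readings are completed and locked before the same examiner sees the CBCT or crown-to-implant images of any patient. Otherwise a different existing examiner reads those.
4. Readings that need the uncropped view are flagged and counted by arm.
5. If this is not done, delete 'blinded' for MBL, CBCT bone thickness and crown-to-implant ratio, and report these readings as unmasked to arm. This costs nothing.

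**Cost of steps 1-4.** Images: 34 × 4 = 136 to 50 × 4 = 200. At an assumed 3-5 minutes each, that is 136 × 3/60 = 6.8 h to 200 × 5/60 = 16.7 h. Adding an assumed 2-4 h of training gives about 9-21 coordinator hours, plus any retakes. No extra visits are needed.

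**Downsides.** Defects deeper than the crop, which are the largest losses, may have to be read unmasked. If the two models look different coronally, masking will be partial.
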